Multicenter RCTs should be conducted in children and adults to determine the benefits or harms of calcitriol or vitamin D analogs in patients with CKD G3a to G5; patient-level outcomes including falls, fractures, sarcopenia, muscle strength, physical function, progression to end-stage kidney disease, cardiovascular events, hospitalizations, and mortality should be assessed. Studies should also include patients with more severe SHPT and should determine the impact of reducing PTH to different target levels, such as the normal range versus higher levels.

KDIGO 2017 Clinical Practice Guideline Update for the Diagnosis, Evaluation, Prevention, and Treatment of Chronic Kidney Disease-Mineral and Bone Disorder (CKD-MBD)

In people with hyperparathyroidism secondary to CKD, does treatment with vitamin D or vitamin D analogues improve patient-related outcomes.

NICE guidelines 2021

In patients with CKD G3b-5, it is currently recommended to monitor the PTH every 3-6 month(3). As more than 50 % of the patients have elevated PTH already at CKD G3b, it is an everyday

consideration for the clinician if the patients should be treated to reduce PTH. This is both time- and cost consuming. At present, there is no evidence to advise if secondary hyperparathyroidism should be treated in patients with CKD.

To improve our knowledge about when secondary hyperparathyroidism should be treated, we want to conduct a randomized clinical trial with one group of patients being treated if PTH is elevated versus a second group of patients not being treated if PTH is elevated.

Hypothesis

We hypothesize that suppression of initially elevated PTH will improve BMD, arterial stiffness, muscle mass and muscle strength in patients with CKD.

Methods and Materials

Subjects will be recruited from the patient population in the outpatient clinic at the Department of Nephrology at Herlev and Gentofte Hospital, Herlev, Denmark.

Study population

Inclusion criteria (all four needs to apply)

1. ≥ 50 years of age at screening
2. CKD G4-5nonD (eGFR < 30 mL/min/1.73m 2) based on local laboratory assessment of serum creatinine and eGFR estimated by the CKD-EPI formula)
3. Plasma PTH $>$ upper normal limit of local laboratory reference range ($> 8,5\mu\text{mol/L}$) and/or treated with active vitamin D (Alphacalcidol) or calcimetics (Cinacalcet) initially
4. Written informed consent

Exclusion criteria

1. Patients who have received a kidney transplant

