A sample size of 70 participants is estimated ($\beta=0.10$; $\alpha=0.05$ (two-sided), drop out 20 % during the study) to detect a difference of 4.9 % change in total hip BMD (effect size) during 18 months.

To ensure that the trial can also provide information about the other fields of interest, we did some statistical considerations about these as well. A minimal relevant difference in the level of PTH after 18 months of intervention is expected to be a difference in PTH of 0.5 times the upper limit of normal range ($8.5 \mu\text{mol}/\text{L}$ (Atellica IM PTH)). PTH has a skewed distribution and thus log transformed to obtain normality. In a population of patients with CKD G4-5 the mean and standard deviation of the logPTH was 1.191 (0.380) (own data, not published). To obtain a difference of 4.25 $\mu\text{mol}/\text{L}$ in PTH = logPTH of 0.628 ($(\beta=0.10$; $\alpha=0.05)$ a sample size of 22 participants is estimated (including drop-out margin of 20%). Based on former studies the sample size should be sufficient to demonstrate a difference of 1 m/s in pulse wave velocity which is considered a difference of clinical relevance for future cardiovascular events(39).

Interventions

The trial is estimated to run for 24 months, as patients will be included during a 6-months period following 18 months follow-up. Following inclusion there will be a 4 weeks run-in period where patients will not be treated with active vitamin D or calcimetics. After run-in patients will be

randomized to either a liberal PTH target ($< 5 \times$ upper normal limit = 42,5 $\mu\text{mol/L}$) or an intensive PTH target (within interval of lower and upper normal limits = 2,0 – 8,5 $\mu\text{mol/L}$). In the intensive PTH target group, treatment will be initiated as soon as the PTH rise above the upper limit of normal. In the liberal PTH target group, treatment will not be initiated until PTH rise above five times the upper limit of normal.

PTH will be measured as intact PTH with Atellica IM PTH assay at Herlev Hospital laboratory (normal range 2,0 – 8,5 $\mu\text{mol/L}$).

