Medications used for management of the disturbances in the mineral metabolism in CKD are native vitamin D, activated vitamin D, phosphate binders and calcimetics. As this is a pragmatic trial embedded in the clinic with usual care, these may be used after the run-in period according to the international guidelines to regulate PTH in the trial cohort (3). All medications for management of disturbances in the mineral metabolism will be registered and reported as part of results.

Study parameters

Baseline characteristics

Age, height, weight, sex, ethnicity(40), smoking status and alcohol use will be registered. Further comorbidity, medical history, biochemical data and medication (including native vitamin D, activated vitamin D, phosphate binders and/or calcimetics) will be collected from participants' medical record and interviews during the trial. The consent will allow the principal investigator, the sponsor and the sponsor's representatives, as well as regulatory authority, direct access to obtain information from the patient's medical records, including electronic records, in order to review information about the trial subject's health condition that is necessary for the conduct of the research project and for control purposes, including self-monitoring, quality control, and monitoring, which they are obligated to perform.

Blood samples

Standard blood samples will be drawn at initiation and month 1, 3, 6, 9, 12 and 18 to measure PTH, ionized calcium, phosphate, creatinine, eGFR, magnesium, haemoglobin, sodium and potassium. 25-hydroxy vitamin D will be measured at initiation and month 3, 9 and 18. Standard blood sample analyses will be run immediately at the local department of clinical biochemistry. Any remaining material after analysis will be destroyed.

For analyses of 1,25-dihydroxy vitamin D, fibroblast growth-factor 23 (FGF23), T50, TRAB5b, bone specific alkaline phosphatase, total alkaline phosphatase and iP1NP, blood samples will be taken at day 0 and at 18 months and stored in the research biobank. PTH will also be measured at in these samples. The biobank will contain samples at -80°C and be analysed in bulk to minimize cost and intra-assay-variability. All residual samples therein will be destroyed after end of study (no later than 1/9-2027).

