Health related quality of life will be evaluated at initiation and after 18 months through questionnaire “Kidney Disease and Quality of Life” (KDQOL-SF1.3, Danish version). The questionnaires will be sent by e-mail or e-boks from the primary investigator to the participants. If an answer has not been received after 14 days a reminder will be e-mailed. If the questionnaire has not been answered 14 days after the reminder, the research team will contact the participant by phone and ask if they need assistance for the questionnaire by the site staff or by receiving it by ordinary mail.

Visit schedule

Visit / Procedure	Visit 1 - >30 days	Visit 2 - <30 days	Visit 3 Day 0	Visit 4 1 month	Visit 5 3 months	Visit 6 6 months	Visit 7 9 months	Visit 8 12 months	Visit 9 18 months
Information	X								
Sign informed consent		X							
Randomization			X						
Screening			X						
Baseline characteristics			X						
Comorbidities, medical history, medication			X						
Standard blood samples			X	X	X	X	X	X	X
25-hydroxy vitamin D			X		X		X		X
Research biobank samples			X						X
DXA-scan			X						X
Pulse wave velocity			X						X

Hand grip strength, 10 meter walk test and sit-to-stand			X							X
Questionnaire			X							X
Bone biopsy										X*
Adverse event collection			X	X	X	X	X	X	X	X

Table 1. Visit schedule. *indicates that it is optional.

For visit 4-8 there will only be taken blood samples with follow-up by phone to minimize time consume for both patient and the investigator. Patients with CKD4-5nonD are usually scheduled in the outpatients clinic 4 times annually, investigators will try to plan the study visits on the same days.

Biobank for future research

There will be established a biobank for future research consisting of 10 ml serum and 8 ml EDTA-plasma from each patient signing the separate informed consent regarding the biobank for future research. The biobank material will be pseudonymised and kept in a locked freezer at -80°C. This is not mandatory for participating in the trial. Patients may at any time contact the primary investigator to have their plasma and serum destroyed. Analyses on the biobank material can only be performed after application and approval by the Ethics Committee System. Samples will be destroyed after 20 years.

Randomisation

Patients will be randomised in a 1:1 ratio to either the intensive PTH target group or the liberal PTH target group for an 18-month period. Randomisation will be performed within computer software.

Blinding

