The trial is investigator-initiated by [name] and will not be initiated before approval from the local scientific ethics committee. The trial will be conducted according to local legislation (*Databeskyttelsesloven*, *Databeskyttelsesforordningen* and *Sundhedsloven*) and Declaration of Helsinki 2013. Further, the trial will be registered at ClinicalTrials.gov before initiated. Since activated vitamin D, calcimetics and phosphate binders are already used to treat hyperparathyroidism and there is no evidence of the optimal PTH-target, the trial is not considered a drug study (correspondence with the Danish Medicines Agency, DMA, case number 2025030893) and will not be monitored by the Good Clinical Practice Unit.

Screening and inclusion

The study will be streamlined and integrated as much as possible into the usual care to reduce the burden on the participants and study staff.

The treating physician in the outpatient clinic at Department of Nephrology may pre-screen the patients for possible enrolment in the study. The pre-screening will involve patients in the outpatient clinic at the Department of Nephrology. Pre-screening will include access to information about age, status on kidney transplant, eGFR, PTH and medication in the patients' medical journal to clarify if patients meet inclusion criteria. Data used for screening patients will be from the time the patient is pre-screened and back to 2015. During trial period there will be pre-screened approximately 500 patients to include 70. The pre-screening process will make the clinicians deliver personal information (personal identification number and telephone number) to the primary investigator prior to the written consent.

Patients meeting the inclusion criteria will be contacted in one of two ways:

- 1) Treating physician giving short information to the patient in the outpatient clinic and the patient giving oral consent to be contacted at telephone by an investigator. Primary investigator will call the patient within 14 days after consent.

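### Is eligibility decided before the 4-week run-in or on Day 0, and does the ambiguity harm the trial?

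*Protocol*

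**What the plan says.** Criterion 3 (Study population) has two routes. One is PTH above the "upper normal limit of local laboratory reference range", given as 8.5; the other is the clause "and/or treated with active vitamin D (Alphacalcidol) or calcimetics (Cinacalcet) initially". Neither route carries a calendar anchor beyond the word *initially*.

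The Interventions section gives the order of events: "Following inclusion there will be a 4 weeks run-in period where patients will not be treated with active vitamin D or calcimetics". Randomisation to a PTH target comes next, in the sentence that opens "After run-in patients will be".

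Screening and inclusion (under Ethics) has the treating physician check age, transplant status, eGFR, PTH and medication in the records against the inclusion criteria. It adds: "Data used for screening patients will be from the time the patient is pre-screened and back to 2015". It also gives the yield: "During trial period there will be pre-screened approximately 500 patients to include 70".

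Table 1 marks consent at the column headed "Visit 2 - <30 days". Its single Screening mark is at Visit 3, Day 0, together with randomisation and the first standard blood sample. The run-in is not shown in the table. The Blood samples section agrees on the sampling: "Standard blood samples will be drawn at initiation and month 1, 3, 6, 9, 12 and 18 to measure PTH".

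**The concern.** Taken at face value, the text decides eligibility before the run-in and the table decides it after. By Day 0 every patient is off active vitamin D and calcimetics, so a check of criterion 3 at that visit could find nobody on treatment. No sentence gives a maximum age for the qualifying PTH or eGFR, and the only period attached to screening data runs back to 2015.

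Two kinds of patient could then be judged differently by two screeners: (a) a treated patient whose Day 0 PTH is 8.5 or lower, and (b) an untreated patient above 8.5 in the records but at or below 8.5 on Day 0. If they are turned away on Day 0, it might be asked whether the 70 counts patients before or after run-in. If they are kept, neither arm starts treatment until PTH rises, so the contrast between arms may be delayed for them.

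**Working it through.** No stated figure can be reproduced here. The sample size inputs (difference 4.9%, SD 5.2%, two-sided alpha 0.05, beta 0.10, 20% drop-out) do not involve the date of eligibility. The check is therefore a comparison of the sections.

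**1. Order of events in the running text.** Records are checked against the criteria, patients who meet them are contacted, consent is signed, inclusion is complete, run-in follows, and randomisation comes last. Screening and inclusion, Interventions and criterion 3 all fit this order.

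**2. Fit with the visit columns.** Written consent is itself an inclusion criterion and is marked at Visit 2. If that column means less than 30 days before Day 0, a run-in of 4 × 7 = 28 days fits between Visits 2 and 3. Apart from the Screening row, Table 1 is compatible with inclusion at Visit 2, then run-in, then Day 0.

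**3. The treatment route.** Read on Day 0, this route would admit nobody, because the run-in has stopped the drugs. A reading that voids half of a criterion is not a serious alternative. *Initially* therefore means before run-in. The phrase *at initiation* in the Blood samples section describes sampling and does not redefine it.

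**4. The two kinds of patient.**

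| Patient | Eligibility before run-in | Day 0 as a second check | What the protocol says |
|---|---|---|---|
| (a) treated, Day 0 PTH ≤ 8.5 | eligible | fails | the and/or wording admits a treated patient whatever the PTH |
| (b) untreated, records > 8.5, Day 0 ≤ 8.5 | eligible | fails | not expressly addressed |

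If either is randomised, both arms have a rule. The intensive arm starts treatment once PTH exceeds the upper normal limit; the liberal arm starts only above five times that limit (5 × 8.5 = 42.5). PTH is measured at months 1, 3, 6, 9, 12 and 18, so a later rise would be seen.

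**5. What the 70 counts.** Study design says that included patients are randomised 1:1. No section has a rule for failing run-in, and the 20% loss is drop-out during the study. The natural reading is 70 randomised.

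**6. Age of the laboratory values.** The sentence on 2015 stands in the paragraph on access to records before consent. It says how far back records may be read, not that a value from 2015 qualifies. The criteria describe present status. The Background cites PTH monitoring every 3–6 months, and the visit schedule section notes about four clinic visits a year (12/4 = every 3 months), so recent values should exist.

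**7. Effect on the comparison.** On either reading eligibility is settled before allocation and by the same rule for both arms. The choice can shift the population slightly, or delay contrast in a few patients. It cannot favour one arm.

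**The case for a change.** The best case for a change is that the Day 0 row may not be a slip. The records check is called pre-screening, which suggests a later, separate screening, and the only one scheduled is on Day 0. Criterion 1 dates age at screening, so the protocol does use that word for an eligibility time point. The first PTH that the trial itself measures is also on Day 0.

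Values near the threshold are also plausible. The protocol gives logPTH a mean of 1.191 and SD of 0.380 in CKD G4-5. The scale is log10, since log10(4.25) = 0.628. With log10(8.5) = 0.929, the limit lies (1.191 − 0.929)/0.380 = 0.69 SD below the mean, within the body of the distribution. Eligibility also cannot be made uniform afterwards for patients already entered.

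Part of this stands. The Screening row is poorly placed or unexplained, the qualifying PTH is undated, and patient (b) is not expressly covered. But the logPTH figures describe a general CKD G4-5 group, not patients selected by criterion 3, and they say nothing about how many would cross the limit over four weeks. The row also follows Randomization in the table, which suits an eligibility gate badly. Figure 1, the visit overview, is not available here and may show the run-in. The extracted table is misaligned in its lower half, so column positions deserve some caution, although the Screening row lies in the better-aligned part.

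**Conclusion.** The inconsistency is real, but it is clerical with a small gap in detail. The criteria, the intervention sequence, the records check and the design statement all point to eligibility before run-in, with included patients going on to randomisation. One table label points the other way. What remains open is whether Day 0 PTH is a second check for untreated patients, and how recent the qualifying values must be. The investigators can settle both in their screening procedure, and either answer leaves a valid randomised comparison.

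The number of patients affected cannot be estimated from the protocol, and no stated figure is wrong because of this point. The conclusion assumes that eligibility is settled before allocation, as the text implies, and that screening relies on recent values, as the monitoring frequency makes practicable. Tidying the Screening row at a routine revision would do no harm, but neither the design nor the analysis depends on it.

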2. Patients receiving treatment with specific anti-osteoporosis medication (denosumab/bisphosphonates) (because of the profound effect on calcium/phosphate fluxes and BMD)

Withdrawal from intervention but continued follow-up (included in intention-to-treat analysis)

1. Withdrawal of consent
2. Kidney transplantation

3. Parathyroidectomy
4. Necessity to initiate dialysis treatment

Patients may withdraw from both intervention and follow-up at any time if desired.

Study design

The REPAIR-CKD trial will be an investigator-initiated pragmatic randomized controlled clinical trial. Included patients will be randomized 1:1 into one of two treatment arms with different targets levels for plasma-PTH: A liberal PTH target ($< 5 \times$ upper normal limit = 42,5 $\mu\text{mol/L}$) or an intensive PTH target (within interval of lower and upper normal limits = 2,0 – 8,5 $\mu\text{mol/L}$) (Figure 1). The cut-off for the liberal PTH target ($< 5 \times$ upper normal limit) was discussed in the national CKD-MBD group. It is chosen to allow the clinician initiate treatment if PTH reaches unusually high levels, no studies have focussed on PTH-targets before, consequently the cut-off is chosen as part of the pragmatic design.

The trial will also pilot the feasibility to obtain a difference in the PTH levels between treatment groups.

[figure not shown]

Figure 1. Visit overview.

Sample size

The primary outcome will be difference in the change in total hip BMD between treatment groups.

In an observational study, the decline in total hip BMD (g/cm^2) was $-1.19\%/\text{year}$ (men) and $-1.51\%/\text{year}$ (women). The decline in men is chosen for a conservative estimate (36). In the dialysis population, the standard deviation (SD) of the one-year decline in BMD is $\pm 5.2\%$ (37). The variance in the BMD change in dialysis patients is expected to be higher than in the CKD population, and therefore this is considered a conservative estimate. Based on these observations the expected decline in BMD in the liberal target group during 18 months is -1.8% (5.2%).

In a previous trial, alendronate was able to increase BMD in total hip by 2.8% during the first year of treatment and 3.4% during 2 years treatment, and thus to increase BMD by 3.1% in 18 months (38). We expect to obtain a similar effect in the intensive target group.

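### On the protocol's own PTH data about one in six patients with elevated PTH may already be above the liberal limit at Day 0; stratify randomisation on this and adjust the primary comparison for it

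*Protocol*

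**What the plan says.** **Entry.** Inclusion criterion 3 asks for PTH above the "upper normal limit of local laboratory reference range" (8.5), and/or existing treatment with active vitamin D or a calcimetic. No upper PTH limit is set. Active vitamin D and calcimetics are withheld for 4 weeks before randomisation.

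**Arms.** Patients are randomised to a PTH target of 2.0–8.5 or of below 42.5. The Study design section says of the higher limit: "It is chosen to allow the clinician initiate treatment if PTH reaches unusually high levels". The Interventions section adds: "In the liberal PTH target group, treatment will not be initiated until PTH rise above five times the upper limit of normal". The Background puts the contrast more sharply, as one group treated for elevated PTH "versus a second group of patients not being treated if PTH is elevated".

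**Data and sample size.** For CKD G4-5, "the mean and standard deviation of the logPTH was 1.191 (0.380) (own data, not published"). The primary sample size takes a mean change of -1.8% for the liberal arm and +3.1% for the intensive arm, a difference of 4.9 points with SD 5.2, and arrives at 70 patients including 20% dropout.

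**Allocation and analysis.** Randomisation is 1:1 by computer software, with no stratification factor named. The Statistics section compares % change in BMD by an unpaired t-test.

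**The concern.** A patient whose PTH is above 42.5 when randomised is beyond the treatment trigger of both arms. If both arms then start PTH-lowering drugs, the arms differ in the target pursued but not in whether treatment is given. The sample size makes no allowance for such patients; it uses one mean for the whole liberal arm.

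Two things are at stake. First, the BMD contrast may be somewhat smaller than planned. Second, in a trial of 70, patients with the highest PTH can fall unevenly between the arms by chance, and neither the randomisation nor the primary test guards against that.

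The text also leaves a gap. The Interventions section describes PTH rising above the limit and does not cover a liberal-arm patient who is already above it at Day 0.

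**Working it through.** **1. Scale of the PTH data.** The Sample size section equates a PTH of 4.25 with "logPTH of 0.628", and log10(4.25) = 0.628, so the logs are base 10. The geometric mean is 10^1.191 = 15.5. On a natural-log scale it would be 3.3, which does not fit a CKD G4-5 cohort.

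**2. Reproducing the plan's own PTH figure.** With difference 0.628, SD 0.380, 90% power and two-sided 0.05, the t-test needs 9 per arm, or 18 in all. Adding 20% gives 18 × 1.2 = 21.6, rounded up to 22, the stated number. Dividing by 0.8 gives 23; the normal approximation gives 20. The mean and SD are therefore being read as intended.

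**3. Share above the liberal limit.** The protocol states: "PTH has a skewed distribution and thus log transformed to obtain normality". Taking log10 PTH as normal:
- P(PTH > 42.5) = 1 − Φ((1.628 − 1.191)/0.380) = 0.125
- P(PTH > 8.5) = 1 − Φ((0.929 − 1.191)/0.380) = 0.754
- P(> 42.5 given > 8.5) = 0.125/0.754 = 0.166, about one in six
- Expected number per arm, if every patient entered with PTH above 8.5: 35 × 0.166 = 5.8

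**4. Sensitivity of the share.** A log mean of 1.10 to 1.30 gives 12% to 23%. An SD of 0.30 to 0.42 gives 9% to 20%.

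**5. Primary sample size.** With 4.9 points, SD 5.2, 90% power and two-sided 0.05, 24 per arm (normal) or 25 per arm (t-test) are needed, which is 60 to 64 in all after 20% dropout. The stated 70 is more than its inputs require. With 70 × 0.8 = 56 evaluable, or 28 per arm, t-test power is 93%.

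**6. Effect on contrast and power.** Let f be the fraction of the assumed effect that liberal-arm patients starting above 42.5 also gain. The documents give no value for f, so a range is shown. Difference = 4.9 × (1 − 0.166f), SD held at 5.2, 28 per arm:

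| f | Difference (points) | Power (t-test) |
|---|---|---|
| 0 | 4.9 | 93% |
| 0.25 | 4.7 | 91% |
| 0.5 | 4.5 | 89% |
| 1 (upper bound) | 4.1 | 82% |

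If the share is 12.5% in place of 16.6%, f = 0.5 gives 4.6 points and 90%, and f = 1 gives 4.3 points and 86%.

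**7. Chance imbalance.** With 35 per arm and no stratification, the SD of the between-arm difference in the share above 42.5 is √(0.166 × 0.834 × 2/35) = 0.089. A two-SD imbalance is about 18 percentage points, or 6 patients (0.18 × 35).

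**The case against.** The strongest reply is that the trial compares two PTH targets. The Purpose, Study design and Interventions sections all say so, and Box 1 asks for the normal range to be compared with higher levels. A patient starting above 42.5 is still assigned to one target or the other. This stands. A reader might infer that the question goes untested in one sixth of patients, but that rests on the single Background sentence and not on the operative design.

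A reader might also infer that a null result could not be told apart from treatment in both arms. The documents do not support this: PTH is measured at months 1, 3, 6, 9, 12 and 18, all mineral-metabolism drugs are registered and reported, and crossovers are to be determined.

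Nor is it stated that these liberal-arm patients are treated from Day 0. That is an inference from the trigger, on which the text is silent.

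The share itself is soft. The data are unpublished, and their treatment status is not given. If part of that cohort was treated, the run-in would raise the share; patients who enter on treatment with normal PTH would lower it. The -1.8% is an arm mean from an observational study not said to be untreated, so it may already contain some treated patients. The 82% case needs patients treated towards below 42.5 to gain the whole effect assumed for 2.0–8.5, which nothing in the protocol supports. These points limit the size of the concern.

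Finally, a restricted analysis is ordinary content for a statistical analysis plan. That is correct. A stratification factor is different: it must be fixed before the first allocation, whereas the analysis plan is due only before data lock.

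**Conclusion.** The point holds as a cheap improvement and not as a flaw that undermines the trial. On the protocol's own figures and a normal log10 PTH, about 12% of CKD G4-5 patients, and about one in six of those above 8.5, would exceed the liberal limit at entry. That sits awkwardly with a limit described as reserved for unusual values, although the protocol does not quantify the term and so does not strictly contradict itself.

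The dilution is modest: a contrast of 4.9 to 4.5 points and power of about 93% to 89%, with 4.1 points and 82% as an upper bound only. The surplus in the 70 patients absorbs most of it. The separation in PTH is hardly threatened: if elevated values are capped at 42.5, the geometric mean is still about 21, against a ceiling of 8.5 in the intensive arm.

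The firmer reason to act is the unprotected chance imbalance in a small trial, on a variable that determines whether the liberal arm's treatment trigger is already met.

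**What to change.** 1. Leave both PTH thresholds and the eligibility criteria unchanged.
2. Stratify the computer randomisation by Day 0 PTH (up to 42.5, above 42.5), with balanced allocation within each stratum.
3. Replace the unadjusted t-test by a comparison of % change in total hip BMD adjusted for that factor.
4. In the Sample size section, state the expected share above 42.5 and the power range as assumptions.
5. Reconcile the trigger wording in Interventions with the rationale in Study design, so that the protocol says how a liberal-arm patient already above the limit at Day 0 is handled. Which rule applies is for the sponsor to decide.

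An analysis restricted to Day 0 PTH above 8.5 and up to 42.5 is optional and supportive only. It would not be a clean comparison of treated with untreated patients, because liberal-arm patients may cross the limit later and native vitamin D and phosphate binders are allowed in both arms.

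**Cost.** Day 0 PTH must be read before allocation; the sample is already scheduled that day and standard samples are run immediately. The primary test changes from a t-test to an adjusted model. The stated power may look slightly less favourable. No extra patients are needed.
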